11.3 Completing Case Report Forms

CRFs from sites must be completed and signed by staff that are listed on the site staff delegation log and authorised by the CI/ PI to perform this duty. The CI/ PI is responsible for the accuracy of all data reported in the CRF.

Once completed the original CRFs must be sent to HRU, UCLH and a copy kept at site. The CRFs must be returned at least weekly of the participant visit. Source data verification of a CRF page should be completed and all data queries answered prior to submission where possible.

11.4 Data handling and analysis

All data will be added to an external validated database hosted by Sealed Envelope.

Data will be reviewed by two independent members of the trial team and presented to the TMG

12 Statistical Considerations

12.1 Outcomes

12.1.1 Primary outcomes

The (binary) primary outcome is whether a 50% reduction (from baseline) has been observed in at least two inflammatory markers (based on CRP, LDH and D dimer) throughout the period of PEX or SOC over a comparable time, following initiation of study.

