To compare the stability of cardiac function based on echocardiogram/troponin/BNP measurements cardiac function between Plasma Exchange (PEX) and control groups in patients with severe COVID

To compare incidence of acute kidney injury as defined by KDIGO criteria between Plasma Exchange (PEX) and control groups in patients with severe COVID

To compare mortality at day 28 between the PEX and control groups

Type of trial: A Phase II, Parallel-group, unblinded, randomised controlled trial in COVID 19

Trial design and methods: Patients will receive standard of care (SOC), or SOC and PEX. Single volume PEX capped at 3 litres if <100Kg and 4 litres if >100Kg. PEX will be given once a day for a minimum of 5 days. The course can be repeated at the discretion of the treating clinician, depending on patient's response based on a reassessment on D5-7, where there is clinical and biochemical improvement following initial 5-day block but persistent pro-thrombotic phenotype ie 5 days initial block plus reassess.

Data collection includes routine laboratory parameters, FBC, renal function and liver function; inflammatory markers (D Dimers, LDH, CRP) and pre and post PEX samples to measure von Willebrand factor (VWF) and ADAMTS13 activity levels. The latter samples will be stored for further investigation related to COVID, for example, COVID19 viral analysis, cytokines.

The control patients will have citrate and serum samples taken daily. Following the initial 5 day period. If patients have more than one 5 block of PEX, comparable daily samples will be taken. Thereafter, weekly to day 28.

Trial duration per participant:	From consent to 28 days
Estimated total trial duration:	From when first participant enrolled to last participant follow-up.
Planned trial sites:	Single-site
Total number of participants planned:	Minimum 20, maximum 40

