6.1 Overall design

This a parallel-group randomised controlled trial, which will be unblinded to the investigators and patients .

Patients will be randomised in a 1:1 ratio to either PEX+SOC or SOC. PEX will be delivered in conjunction with standard of care in all patients as dictated by the treating clinicians.

PEX will be given for a minimum of 5 days, but the course can be repeated depending on patient's response, based on a reassessment on D5-7. The 5 day PEX will be repeated at the discretion of the treating clinician in patients showing clinical and biochemical improvement but a persistent pro-thrombotic phenotype following the initial 5-day block .

Patients will be followed up until 28 days post treatment.

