9.1 Pre-treatment Assessments

All cases screened for the study will be captured and reason for not being recruited documented.

The following trial specific procedures will be carried out after consent:

1. Demographics recorded including gender, age, height, weight, race
2. Medical History recorded to exclude underlying pre morbid conditions, VTE history, Smoking history
3. General physical examination
4. Concomitant Medication recorded: Primarily antibiotics, noradrenaline use
5. Blood tests
 - Serum pregnancy test (for women of child bearing potential) in last 7 days
 - Baseline inflammatory parameters and routine bloods (FBC, renal, liver function and coagulation screen with fibrinogen, LDH, CRP, D dimer, ferritin)
 - Hepatitis A, B, C and HIV pre PEX (result does not need to be available before PEX)
 - Troponin T/BNP (result does not need to be available before PEX)
 - C3/4 (result does not need to be available before PEX)
 - Autoimmune screen (ANA, ENA) (result does not need to be available before PEX)
 - Factor VIII, VWF, ADAMTS-13 activity (result does not need to be available pre PEX)
 - IgG and IgM to COVID-19 (result does not need to be available before PEX)
 - PCR result for COVID-19 (result does not need to be available before PEX, see inclusion criteria for definition of probable COVID))
6. Respiratory parameters: SaO₂, RR
 - PaO₂, FiO₂
 - Method of assisted ventilation eg HDNOHFNO, CPAP
 - P:F ratio
 - CXR/ CT/HRCT : if undertaken as part of routine clinical care
7. Cardiac investigations
 - ECG (result does not need to be available before PEX)

- Echocardiography (if available within 48 hours of enrolment to study)

The results from the following routine procedures may be used:

Blood test results within 48 hours of enrolment

PCR result for COVID-19 within past 14 days (result does not need to be available before PEX, see inclusion criteria for definition of probable COVID)

Pregnancy test within 7 days

Where routine results are not available, the procedure(s) will be carried out at screening after consent.

All pre-treatment procedures will be carried out as specified in the schedule of assessments (**appendix 2**).

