9.4 Subsequent assessments and procedures

9.4.1 Visit schedule and assessments

A schedule of all trial assessments and procedures is set-out in **Appendix 3**.

Day 1- 5

- eligibility check pre PEX if randomised to PEX
- Vitals pre and post PEX (temperature, blood pressure, pulse, respiratory rate and oxygen saturation level) or once daily
- Plasma exchange if randomised to PEX
- assessment of compliance with PEX
- general physical examination
- recording of relevant concomitant medications eg start stop dates of antibiotics, noradrenaline
- Daily routine bloods (FBC, renal, liver function and coagulation screen with fibrinogen)
- Inflammatory markers on D1,D3 &D5 (LDH, CRP, D dimer, ferritin)
- Citrated plasma and serum samples pre and post PEX, or daily for those randomised to SOC to save for VWD screen, ADAMTS13 activity, COVID-19 serology, and multiplex inflammatory markers related to ILs cytokines, interferons, and vascular markers of endothelial injury. Spare samples can be used for COVID-19 related research as authorised by the trial team
- Respiratory parameters: Oxygen requirement, respiratory rate, type of ventilator support-as part of standard of care assessment
- Echocardiogram on D1
- Troponin and BNP on D1
- adverse event collection
- Reactions to Plasma exchange: graded 1-4
- Complications related to central vascath
- Need for antibiotics
- Deterioration requiring ventilation
- Arterial or venous thrombotic event

Reassessment (Day 5-7)

Review of clinical and laboratory parameters by trial team. Consideration of further 5 day block of PEX if clinical and biochemical improvement following initial 5-day block but persistent pro-thrombotic phenotype

*If a patient has a second 5 days of PEX started-follow instructions for day 1-5 above

Follow up Day 6 - 28*

- Vitals (temperature, blood pressure, pulse, respiratory rate)
- general physical examination-weekly
- recording of concomitant medications-related to antibiotics, new cardiac medication, but not all the routine medicines re SOC and not including PRN medications.
- Daily routine bloods (FBC, renal, liver function and coagulation screen with fibrinogen)
- Inflammatory markers, at least 3 x/week (LDH, CRP, D dimer, ferritin)

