9.8. Discontinuation/withdrawal of participants

Discontinuation of Trial Treatment for clinical reasons

A participant may be withdrawn from trial treatment whenever continued participation is no longer in the participant's best interests, but the reasons for doing so must be recorded. Reasons for discontinuing treatment may include

disease progression whilst on therapy

unacceptable toxicity: **anaphylaxis to plasma**

intercurrent illness which prevents further treatment

patients withdrawing consent to further trial treatment

Any alterations in the participant's condition which justifies the discontinuation of treatment in the site investigator's opinion

Persistent non-compliance to protocol requirements

The decision to withdraw a participant from treatment must be recorded in the CRF and medical notes, and the sponsor when required should be notified in writing.

In these cases participants remain within the trial for the purposes of follow-up for safety and or data analysis according to the treatment option to which they have been allocated

Participant withdrawal from trial treatment

If a participant expresses their wish to withdraw from trial treatment, sites should explain the importance of remaining on trial follow-up and seek permission to allow use of routine follow-up data to be used for trial purposes. The importance of safety follow-up should be emphasised to the participant in the Participant Information Sheet.

The decision of the participant to withdraw from treatment must be recorded in the CRF and medical notes.

The participant may withhold their reason for withdrawal however, if the participant gives a reason for their withdrawal, this should be recorded.

Withdrawal of Consent to Data Collection

If a participant explicitly states they do not wish to contribute further data to the trial their decision must be respected and recorded in the CRF and medical notes.

Loss to follow-up

If a participant moves from the area, every effort should be made for the participant to be followed up at another participating trial site and for this new site to take over the responsibility for the participant.

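### The primary outcome is read over a PEX period whose length can depend on each patient's response, with no rule for extended or shortened courses and no scoring rule; one common scheduled day would settle it

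*Combined protocol and SAP*

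**What the plan says.** Section 12.1.1 asks whether a 50% reduction from baseline has been observed in at least two of CRP, LDH and D-dimer "throughout the period of PEX or SOC over a comparable time, following initiation of study". Neither the synopsis nor section 12.4.2 adds a day.

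The length of the PEX period is set elsewhere:

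- Section 6.1 gives a minimum of 5 days, with reassessment on D5-7, and allows more: "The 5 day PEX will be repeated at the discretion of the treating clinician in patients showing clinical and biochemical improvement", provided a pro-thrombotic phenotype persists. Section 9.4.1 says much the same: "Consideration of further 5 day block of PEX if clinical and biochemical improvement following initial 5-day block but persistent pro-thrombotic phenotype".
- Section 9.8 lets treatment stop early, for example for "disease progression whilst on therapy", and adds that "participants remain within the trial for the purposes of follow-up".
- Section 6.1 describes the trial as one "which will be unblinded to the investigators and patients".

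On matching the arms, the synopsis says "If patients have more than one 5 block of PEX, comparable daily samples will be taken". Sections 9.4.1 and Appendix 3 schedule the markers on D1, D3 and D5 in both arms, and Appendix 3 also names D7.

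On baseline, section 9.1 lists baseline inflammatory parameters among the pre-treatment assessments and accepts routine "Blood test results within 48 hours of enrolment". Section 9.4.1 has a further D1 draw.

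**The concern.** A binary outcome of this kind depends on how long and how often one looks. If any qualifying draw counts, a longer window gives more chances to respond. If the fall must be sustained, a longer window gives more chances to lose the response. The window should therefore be the same in both arms and fixed in advance.

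Here it is tied to treatment duration. Extension is open only to PEX patients, requires biochemical improvement, and is decided by clinicians who know the allocation. Biochemical improvement overlaps with an endpoint built from CRP, LDH and D-dimer. Early stopping for progression pulls the window the other way.

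The reference to a comparable time shows that matching was intended. But SOC patients are randomised in blocks and are not paired with PEX patients. If some PEX patients have 5 days, some 10 and some fewer than 5, nothing says which window a given SOC patient receives. That choice, and the choice between first, last and sustained response, would be made later by people who know the allocation, on the only primary outcome and with at most 20 patients per arm.

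**Working it through.** **The plan's own figures.** Section 12.2.1 gives power of 80% (80% v 20%, 20 patients), 99% (80% v 20%, 40 patients) and 85% (65% v 20%, 40 patients). With n per arm, d the difference and p̄ the mean rate, two-sided 5%:

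power = Φ{[d − 1.96·√(2p̄(1−p̄)/n)] / √[(p₁(1−p₁)+p₂(1−p₂))/n]}

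- n=10, 80% v 20%: (0.600 − 0.438)/0.179 = 0.90, power 81.7%
- n=20, 80% v 20%: (0.600 − 0.310)/0.126 = 2.29, power 98.9%
- n=20, 65% v 20%: (0.450 − 0.306)/0.139 = 1.03, power 84.9%

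Exact enumeration of the uncorrected chi-squared test gives 80.5%, 98.2% and 84.1%. The stated power reproduces, so the problem is in the outcome definition and not in the sample size arithmetic. The rates do need a day: if the SOC rate on the chosen day were 30% (an assumption), the three powers would be 63.0%, 92.1% and 60.8%.

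**What unequal windows could do.** This is an illustration only. From the plan: a 20% SOC response, 20 or 10 per arm, and the chi-squared test. A second block that starts on D6 to D8 ends on D10 to D12. Assumed, and not in the documents: no treatment effect, the 20% holds by day 5, constant hazard, SOC read at day 5, a share f = 25% of the PEX arm extended and read to the end of the second block, and first-hit scoring. Let r be the share of extended patients who had already responded by day 5.

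- Chance g that a day-5 non-responder responds later: by D10, 1 − 0.8^(5/5) = 0.200; by D12, 1 − 0.8^(7/5) = 0.268.
- PEX response = 0.20 + f(1 − r)g.
- r cannot exceed 0.20/0.25 = 0.8 on average.

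Exact rejection rates at 20 per arm, against SOC at 0.20:

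| r | PEX response | PEX-favouring | Total two-sided |
|---|---|---|---|
| 0.8 | 0.210–0.213 | 3.0–3.2% | 5.1–5.2% |
| 0.5 | 0.225–0.234 | 3.9–4.4% | 5.4–5.8% |
| 0.2 (extension unrelated to response) | 0.240–0.254 | 4.9–6.0% | 6.1–6.9% |
| 0 | 0.250–0.267 | 5.7–7.2% | 6.7–7.9% |
| Equal windows, day 5 | 0.200 | 2.5% | 5.0% |

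At 10 per arm the same cases total 3.1–4.4%, against 3.0% with equal windows.

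**The opposite direction, 20 per arm.**

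- Early stopping: if 10% to 25% of the PEX arm stopped early and were read at day 2 or 3, their response would be 1 − 0.8^(2/5) = 0.085 or 1 − 0.8^(3/5) = 0.125. The PEX arm would be at 0.171–0.193, SOC-favouring error 2.9–4.2% and total error 5.1–5.6%.
- Sustained scoring, 25% extended, half of the responders among them losing response: PEX response = 0.20 − 0.25·r·0.5 = 0.175 (r=0.2) or 0.1375 (r=0.5). SOC-favouring error is 3.9% or 7.4%, and total error 5.5% or 8.1%.

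**Equal windows of any length.** With both arms read at day 5, 7, 10 or 12, the error per direction is 2.3–2.6%. The inflation comes from the inequality and not from the length.

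**The case against.** The strongest reply is that the plan already supplies a window. The Day 1-5 list in section 9.4.1 is written for both arms and schedules the markers on D1, D3 and D5. For a PEX patient given one full block, D1-5 is the obvious reading, and a SOC patient has the same draws. This stands. A reader might infer that no SOC patient can be scored at all; the documents do not support that. The gap concerns extended and shortened courses, and the scoring rule for everyone.

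Three further points also stand, in part or in full:

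- Baseline is mostly answered, because section 9.1 labels a pre-treatment sample. Only its precedence over the D1 draw is open.
- Reading early stoppers at day 2 or 3 is an assumption. Section 9.8 keeps them in follow-up and section 12.4.2 specifies intention to treat. Neither says on which day they are scored.
- Extension requires improvement, so extended patients are probably enriched for those who have already responded. That makes the rows with low r less plausible. They are not excluded, since improvement need not mean a 50% fall in two markers.

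The comparable-time wording and the synopsis sentence on comparable samples do not close the gap. The first states an intention, and the second governs sampling and not scoring.

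**Conclusion.** The concern holds for the definition of the outcome. The scoring window for PEX can depend on post-randomisation response that overlaps with the endpoint. No window is assigned to either arm when a course is extended or cut short, and the scoring rule is unstated.

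The size is unknown. Under the assumptions above, extension gives a total error of 5.1–7.9% against 5.0% at 20 per arm, with PEX-favouring error of 3.0–7.2% against 2.5%. The lower end is more plausible, and at 10 per arm the total stays below 5%. The share extended, the constant hazard and the scoring rule are all assumed.

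A reader might infer that the design favours PEX. The documents do not support a direction: first-hit scoring over a longer PEX window favours PEX, while sustained scoring, or a shorter window after early stopping, works against it. The case for change rests on the text of the definition and not on these error rates.

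**What to change.** Rewrite section 12.1.1 so that response means at least a 50% fall from one stated baseline sample in at least two of CRP, LDH and D-dimer, all read on one fixed, already scheduled day. The day should be the same in both arms, counted from one common anchor, and apply regardless of exchanges given, early stopping or a further block. The team should choose and justify it: D5 is named in both section 9.4.1 and Appendix 3, D7 only in Appendix 3.

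Also state:

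- which sample takes precedence as baseline, the pre-treatment sample in section 9.1 or the D1 draw;
- when the marker sample is taken relative to any exchange that day;
- how death, discharge or a missing sample is scored;
- that the 80%, 65% and 20% rates in section 12.2.1 refer to that day.

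Use the same day for the VWF/ADAMTS13 outcome in section 12.1.2, which now ends with PEX, a point SOC patients never reach.

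The cost is wording in sections 12.1.1, 12.1.2 and 12.2.1, with matching lines in the schedule. There are no new blood draws and no change to who receives a further block. If the existing rates apply on the chosen day, power is unchanged.

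There are two downsides. Responses after the chosen day become descriptive. And each candidate day has a drawback: a D5 sample taken before that day's exchange reads the outcome after four of the five exchanges, which may lower the assumed PEX response rate, while a D7 reading follows the full first block but may fall within a further one.

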12.1.2 Secondary outcomes

1. Number of patients requiring mechanical ventilation who required only supplemental O₂/CPAP at study entry. This will be captured throughout the period of the study, by review of the oxygen requirements and ventilatory support required throughout the study (O₂ requirement or PaO₂:FiO₂ (P:F ratio) sequentially)
2. 50% decrease in VWFAg/ADAMTS 13 activity ratio from baseline to end of PEX.
3. Prevent deterioration in myocardial function on ECHO/ cardiac parameters -monitoring of cardiac function through echocardiogram and/ or BNP and Troponin levels throughout study period
4. Clinical thrombotic events documented by imaging either venous DVT/PE, or arterial thrombus (cardiac, neurological and peripheral vascular) throughout the study period
5. Incidence of acute kidney injury as defined by KDIGO criteria throughout study period
6. Mortality at 28 days

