To compare rates of mechanical ventilation between Plasma Exchange (PEX) and control groups in patients with severe COVID requiring CPAP/ NIV at treatment onset

To compare rates of clinical thrombotic events either venous (deep vein thrombosis DVT or pulmonary embolism PE) or arterial thrombus (cardiac, neurological and peripheral vascular) between Plasma Exchange (PEX) and control groups in patients with severe COVID

To compare reduction in the inflammatory-thrombotic response by monitoring von Willebrand factor VWF antigen/ADAMTS 13 activity ratio between Plasma Exchange (PEX) and control groups in patients with severe COVID

To compare the stability of cardiac function based on echocardiogram/troponin/BNP measurements between Plasma Exchange (PEX) and control groups in patients with severe COVID

To compare incidence of acute kidney injury as defined by KDIGO criteria between Plasma Exchange (PEX) and control groups in patients with severe COVID

To compare mortality at day 28 between the PEX and control groups

6 Trial design

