12.4.3 Secondary outcome analysis

Secondary outcomes will be summarised and compared using suitable statistical methods. For example, binary outcomes may be compared using chi-squared tests and numerical outcomes may be compared using t-tests. P-values from tests of secondary outcomes may be adjusted to account for multiple testing. Appropriate regression methods will be used to perform adjusted analyses or to account for repeated measures.

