12.4.4 Sensitivity and other planned analyses

The level of missing data will be reported and sensitivity and/or adjusted analyses performed to account for missing data.

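### Secondary outcome 1 scores a death without mechanical ventilation as a non-event, so an arm with more such deaths could look better on ventilation

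*Combined protocol and SAP*

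**What the plan says.** Secondary outcome 1 in section 12.1.2 is "Number of patients requiring mechanical ventilation who required only supplemental O₂/CPAP at study entry". It is to be captured "by review of the oxygen requirements and ventilatory support required throughout the study", that is, from oxygen and ventilator records. The matching objective in section 5 is "To compare rates of mechanical ventilation between Plasma Exchange (PEX) and control groups in patients with severe COVID requiring CPAP/ NIV at treatment onset". Neither text mentions death.

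Death appears as a separate item in the same list, "Mortality at 28 days", and is not combined with ventilation.

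On analysis, section 12.4.3 gives only an example: "binary outcomes may be compared using chi-squared tests". Section 12.4.4 adds "The level of missing data will be reported and sensitivity and/or adjusted analyses performed to account for missing data", which does not say whether a patient who has died counts as missing, as an event or as a non-event. The plan contains no composite outcome, no ventilator-free-survival definition and no competing-risk method.

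**The concern.** Death without ventilation removes the chance of being ventilated later. If the outcome counts only ventilated patients, that death is recorded in the same cell as a recovery on oxygen. The comparison then mixes a good and a very bad result among its non-events, and the mix may differ between arms.

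At stake is the direction of the ventilation comparison. With at most 20 patients per arm (section 12.2.1), and fewer once those already ventilated at entry are set aside, one unventilated death is at least 1/20 = 5 percentage points of an arm. The outcome tables also carry more weight than usual here. Section 10.5 exempts intubation and COVID-19 death from adverse event capture, so safety reporting will not give a second structured comparison of them.

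**Working it through.** **Figures in the plan.** No rate or power is stated for the ventilation outcome. The Table 1 percentages that come with counts agree with them: 22/52 = 42%, 19/22 = 86.4%, 18/24 = 75%, 9/18 = 50%, 2/13 = 15%. The overall mortality column gives percentages with the counts left blank.

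**Step 1: deaths without ventilation in Table 1.** Overall deaths = mortality % × ICU cases. Deaths without ventilation = overall deaths − deaths among ventilated patients. Where the latter are not reported, the lower bound is max(0, deaths − number ventilated) and the upper bound is min(deaths, number not ventilated).

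| ICU cases | Overall deaths | Ventilated | Deaths on ventilation | Deaths without ventilation | Share of deaths |
|---|---|---|---|---|---|
| 52 | 0.61 × 52 = 31.7, so 32 | 22 | 19 | 32 − 19 = 13 | 13/32 = 41% |
| 24 | 0.50 × 24 = 12 | 18 | 9 | 12 − 9 = 3 | 3/12 = 25% |
| 13 | 0.38 × 13 = 4.9, so 5 | 2 | not reported | at least 5 − 2 = 3 | at least 3/5 = 60% |
| 36 | 0.17 × 36 = 6.1, so 6 | 17 | not reported | 0 to 6 | not informative |
| 21 | 0.67 × 21 = 14.1, so 14 | 15 | not reported | 0 to 6 | not informative |
| 1591 | 0.26 × 1591 = 413.7, so 414 | 1150/1300 × 1591 ≈ 1407 | not reported | 0 to 184 | not informative |

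The first three rows together give at least 13 + 3 + 3 = 19 of 32 + 12 + 5 = 49 deaths. Among patients never ventilated, 13/30 = 43% died in the 52-patient row and 3/6 = 50% in the 24-patient row.

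**Step 2: how far the time horizon matters.** Section 3 gives 28 days for the deaths among ventilated patients in the 52-patient cohort; no horizon is stated for overall mortality. If every ventilated patient had eventually died, the floor would be 32 − 22 = 10 in the 52-patient row and 0 in the 24-patient row (12 deaths, 18 ventilated). The 13-patient row stays at 3, because that figure is already such a floor.

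**Step 3: effect of counting death as an event.** Using the Step 1 counts, ventilation alone against ventilation or death is:
- 52-patient row: 22/52 = 42% becomes 35/52 = 67%.
- 24-patient row: 18/24 = 75% becomes 21/24 = 87.5%.
- 13-patient row: 2/13 = 15% becomes at least 5/13 = 38%.

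**Step 4: illustration with assumed numbers.** Take 20 patients per arm, none ventilated at entry. PEX has 5 ventilated and 4 dead unventilated; SOC has 8 ventilated and 1 dead unventilated. The outcome as written gives 25% v 40%, a 15-point advantage for PEX. Ventilation or death gives 9/20 v 9/20, no difference.

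**Step 5: what is not affected.** The power statements in section 12.2.1 concern the primary outcome. With power = Φ[(|p₁ − p₂| − 1.96√(2p̄(1 − p̄)/n)) / √((p₁(1 − p₁) + p₂(1 − p₂))/n)], the results are 81.7% (80% v 20%, n = 10 per arm), 98.9% (same rates, n = 20) and 84.9% (65% v 20%, n = 20). The plan states 80%, 99% and 85%. These reproduce within 2 points and do not depend on this outcome.

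**The case against.** **The populations differ.** Table 1 describes ICU cohorts with no stated limit on escalation. This trial admits patients from more than 2 L/min of oxygen and excludes those with significant comorbidity whose escalation is limited to CPAP (sections 8.1.1 and 8.1.2), the group most likely to die unventilated. This stands: Table 1 cannot be carried over as a rate for this trial. It does not close the gap, because the exclusion does not cover sudden death. Section 3 itself reports pulmonary embolism as the direct cause of death in 4 of 12 autopsied patients.

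**Mortality is reported separately.** In a trial of at most 40 patients, an excess of deaths would be seen beside the ventilation result. That is true, and it limits the harm. It does not change the ventilation estimate or its p-value, and separate totals do not show which deaths were unventilated.

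**The plan does not commit to a crude test.** The chi-squared test is offered as an example and regression is also foreseen. This is correct, but the gap lies in the outcome definition, and any method applied to it inherits the scoring.

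**The illustration is invented and not significant.** Also correct: 5/20 v 8/20 gives an uncorrected chi-squared p of about 0.31. It shows the possible direction of distortion, not a likely false positive.

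**A cross-tabulation would be enough.** Tabulating ventilation by death would expose the problem without redefining anything. That table is needed in any case, but alone it leaves the formal comparison on the flawed count.

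**Conclusion.** The point holds for secondary outcome 1. As worded, death without ventilation is a non-event, and an arm with more such deaths could look better.

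The protocol's own figures make such deaths plausible: about 13 of 32, 3 of 12 and at least 3 of 5 deaths in the three informative rows of Table 1. This rests on rounded percentages with blank counts and, for the first two rows, on a shared time horizon. The rate in this trial should be lower and is not documented.

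Three stronger readings might be inferred, and the documents do not support them:

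- *That Table 1 reports many unventilated deaths, or predicts them here.* It prints none. They are obtained by subtraction, three of six rows allow zero, and the populations differ.
- *That the plan classes these deaths as successes.* It is silent on death; the favourable scoring follows from the wording of the outcome.
- *That acute kidney injury and thrombosis need a competing-risk analysis on the same grounds.* The kidney outcome, "Incidence of acute kidney injury as defined by KDIGO criteria throughout study period", is also silent on death. But follow-up is fixed at 28 days and section 10.9 describes participants as hospitalised throughout, so little censoring is expected. Without censoring, the day-28 cumulative incidence with death as a competing event equals events/N, the same crude proportion. The method would not change those results.

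This is a moderate weakness in one secondary outcome of a small phase II trial, worth correcting before analysis.

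**What to change.** In section 12.1.2, define secondary outcome 1 as mechanical ventilation or death by day 28, in patients not mechanically ventilated at randomisation, and compare this between arms. Beside it, report by arm the number ventilated and the number who died without ventilation. The ventilation row then still answers the section 5 objective of comparing ventilation rates.

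The cost is a wording change to the outcome and one extra table, settled before the data are analysed. No new data are needed: changes in respiratory support are in the Appendix 3 schedule, and 28-day mortality is recorded at the end-of-study assessment in section 9.4.1. The downside is that the composite mixes two events of different weight, which is why both components must be shown. No change is proposed to the kidney injury or thrombosis outcomes, the primary outcome or the sample size.
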